5.4.5. Renal Stopping Criteria

The presence of any of the following which are reasonably attributable to GSK3039294 will be nominally categorised as a severe adverse event and will constitute individual stopping criteria for subjects:

Healthy volunteers (Part A or Part B):

- Spot Urine Protein Creatinine (UPC) ratio > 0.5

Healthy volunteers (Part A or Part B) & Patients (Part C):

- Increase in serum creatinine (Δ sCr) of 0.3 g/dL from baseline (or an increase of 50% at any time if the baseline is > 0.6 g/dL)
- Detectable glycosuria in the presence of concomitant normoglycaemia

- Hypophosphataemia (less than 0.8mmol/L)
- Metabolic acidosis

All abnormal results should be confirmed within 24 hours before individual subject stopping criteria are implemented.

5.4.6. Stopping Criteria Based On Disease Progression in Systemic Amyloidosis Patients in Part C

In Part C, individual systemic amyloidosis patients can be withdrawn at any time during the study where the investigator has a reasonable level of clinical suspicion that the patient's underlying systemic amyloidosis is worsening (including worsening cardiac dysfunction in those patients known to have cardiac amyloid involvement). In this setting, the investigator in consultation with the Medical Monitor must refer the patient to their primary hospital physician for further consultation and appropriate diagnostic tests

5.5. Stopping Criteria for the Entire Healthy Volunteer or Patient Study Groups

- If an SAE occurs that the investigator believes is reasonably attributable to IMP, in any subject at any one dose level of GSK3039294, continuation of the study will be temporarily halted and no further subjects will be dosed until a full safety review of the data has taken place.
- If the same severe adverse event is observed in two subjects across all study parts, and is reasonably attributable, in the opinion of the investigator, to GSK3039294, the study will be temporarily halted and no further subjects will be dosed until a full safety review of the study has taken place.
- If the study is temporarily halted, relevant reporting and discussion with the Medical Monitor, relevant GSK personnel, and with the applicable regulatory authority will take place prior to any resumption of dosing
- Every effort will be made to take a blood sample for pharmacokinetic analysis from each affected individual at the time of any of the adverse events described above

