5.4. Withdrawal/Stopping Criteria

The following actions must be taken in relation to a subject who fails to attend the clinic for a required study visit:

- The site must attempt to contact the subject and re-schedule the missed visit as soon as possible.
- The site must counsel the subject on the importance of maintaining the assigned visit schedule and ascertain whether or not the subject wishes to and/or should continue in the study.
- In cases where the subject is deemed 'lost to follow up', the investigator or designee must make every effort to regain contact with the subject (where possible, 3 telephone calls and if necessary a certified letter to the subject's last known mailing address or local equivalent methods). These contact attempts should be documented in the subject's medical record.
- Should the subject continue to be unreachable, only then will he/she be considered to have withdrawn from the study with a primary reason of "Lost to Follow-up".

Non-compliance to the study regimen or withdrawal of consent (no reason has to be given by the individual subject) will lead to the removal from the study. An individual subject may withdraw from study treatment at any time at his/her own request, or may be withdrawn at any time at her own request, or at the discretion of the investigator for safety, behavioural or administrative reasons. If a subject withdraws from the study, he/she may request destruction of any samples taken, and the investigator must document this in the site study records. The entire study will be terminated if the sponsor (GSK) stops the study at any stage.

Individual subjects may be withdrawn at the investigator's discretion at any time during the study, provided there is a valid and confirmable clinical reason. The presence of severe AEs predefined as stopping criteria below in Section 5.5, or SAE as defined in [Appendix 3](#), will lead to the withdrawal of an individual subject. Withdrawn subjects will be replaced by new subjects as per the guidance in Section 6.4

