5.4.2. Liver Chemistry Stopping Criteria

Liver chemistry stopping and increased monitoring criteria have been designed to assure subject safety and evaluate liver event etiology (in alignment with the FDA premarketing clinical liver safety guidance).

<http://www.fda.gov/downloads/Drugs/GuidanceComplianceRegulatoryInformation/Guidances/UCM174090.pdf>

Study treatment will be discontinued **for a healthy volunteer subject in Part A or B, or a systemic amyloidosis patient without liver involvement /no biochemical liver dysfunction in Part C** with baseline liver chemistry within the normal reference range for ALT if they are reasonably attributable to GSK3039294 and provided the following liver chemistry stopping criteria are met:

Phase I Liver Chemistry Stopping Criteria – Liver Stopping Event Algorithm

In Part C, systemic amyloidosis patients will be required to return for follow-up liver chemistry assessments within 1 week of the changes from the baseline liver chemistry at Day -1 (see [Table 6](#)) being reported. Individual systemic amyloidosis patients will be withdrawn from the study if the following liver chemistry changes are reported from baseline at Day -1 (see [Table 6](#)).

Table 6 Change from baseline in liver chemistry for repeat or withdrawal

Baseline Liver Chemistry	Repeat assessment within 1 week	Withdrawal
x1 ULN < ALT ≤ x3 ULN Bilirubin ≤ x1ULN	ALT > x4 ULN Bilirubin > x 1.5 ULN	ALT > x6 ULN Bilirubin > x 1.5 ULN
x1 ULN < ALT ≤ x3 ULN Bilirubin ≤ x1.5 ULN	ALT > x4 ULN Bilirubin > x 2 ULN	ALT > x6 ULN Bilirubin > x 2 ULN

Liver Safety Required Actions and Follow up Assessments Section can be found in [Appendix 2](#) (Section 12.2)

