5.4.3. QTc Stopping Criteria

Healthy Volunteers & Amyloidosis Patients:

A healthy volunteer or patient that meets either bulleted criterion below will be withdrawn from the study.

- QTcF > 500 msec,
- Change from baseline in healthy volunteer subjects: QTcF >60 msec

For patients with underlying **bundle branch block**, follow the discontinuation criteria listed below:

Baseline QTcF with Bundle Branch Block	Discontinuation QTcF with Bundle Branch Block
< 450 msec	> 500 msec
450 – 480 msec	≥ 530 msec

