12.2. Appendix 2: Liver Safety Required Actions and Follow up Assessments

Phase I Liver chemistry stopping criteria have been designed to assure subject safety and to evaluate liver event etiology (in alignment with the FDA premarketing clinical liver safety guidance).

<http://www.fda.gov/downloads/Drugs/GuidanceComplianceRegulatoryInformation/Guidances/UCM174090.pdf>.

12.2.1. Healthy Volunteers:

Phase I liver chemistry stopping criteria and required follow up assessments

Liver Chemistry Stopping Criteria – Liver Stopping Event	
ALT-absolute	
ALT\geq3xULN
 
If ALT\geq3xULN AND bilirubin^{1,2} \geq 2xULN (>35% direct bilirubin) or INR >1.5, Report as an SAE.
 
See additional Actions and Follow Up Assessments listed below

Required Actions and Follow up Assessments following Liver Stopping Event	
Actions	Follow Up Assessments

 • Immediately discontinue study treatment • Report the event to GSK within 24 hours • Complete the liver event CRF, and complete an SAE data collection tool if the event also meets the criteria for an SAE² • Perform liver event follow up assessments • Monitor the subject until liver chemistries resolve, stabilise, or return to within baseline (see MONITORING below) 
MONITORING:
 
If ALT\geq3xULN AND bilirubin \geq 2xULN or INR >1.5
 
 • Repeat liver chemistries (include ALT, AST, alkaline phosphatase, bilirubin) and perform liver event follow up assessments within 24 hrs • Monitor subjects twice weekly until liver chemistries resolve, stabilise or return to 	
 • Viral hepatitis serology³ • Blood sample for pharmacokinetic (PK) analysis, obtained within 48 hours of last dose⁴ • Serum creatine phosphokinase (CPK) and lactate dehydrogenase (LDH). • Fractionate bilirubin, if total bilirubin\geq2xULN • Obtain complete blood count with differential to assess eosinophilia • Record the appearance or worsening of clinical symptoms of liver injury, or hypersensitivity, on the AE report form • Record use of concomitant medications on the concomitant medications report form including acetaminophen, herbal remedies, other over the counter medications. • Record alcohol use on the liver event

Liver Chemistry Stopping Criteria – Liver Stopping Event	

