12.4.4. Evaluating AEs and SAEs

Assessment of Intensity

The investigator will make an assessment of intensity for each AE and SAE reported during the study and will assign it to one of the following categories:

- Mild: An event that is easily tolerated by the subject, causing minimal discomfort and not interfering with everyday activities.
- Moderate: An event that is sufficiently discomforting to interfere with normal everyday activities
- Severe: An event that prevents normal everyday activities. - an AE that is assessed as severe will not be confused with an SAE. Severity is a category utilized for rating the intensity of an event; and both AEs and SAEs can be assessed as severe.
- An event is defined as 'serious' when it meets at least one of the pre-defined outcomes as described in the definition of an SAE.

Assessment of Causality

- The investigator is obligated to assess the relationship between study treatment and the occurrence of each AE/SAE.
- A "reasonable possibility" is meant to convey that there are facts/evidence or arguments to suggest a causal relationship, rather than a relationship cannot be ruled out.
- The investigator will use clinical judgment to determine the relationship.
- Alternative causes, such as natural history of the underlying diseases, concomitant therapy, other risk factors, and the temporal relationship of the event to the study treatment will be considered and investigated.
- The investigator will also consult the Investigator Brochure (IB) and/or Product Information, for marketed products, in the determination of his/her assessment.
- For each AE/SAE the investigator **must** document in the medical notes that he/she has reviewed the AE/SAE and has provided an assessment of causality.
- There may be situations when an SAE has occurred and the investigator has minimal information to include in the initial report to GSK. However, **it is very important that the investigator always make an assessment of causality for every event prior to the initial transmission of the SAE data to GSK.**
- The investigator may change his/her opinion of causality in light of follow-up

information, amending the SAE data collection tool accordingly.

- The causality assessment is one of the criteria used when determining regulatory reporting requirements.

Follow-up of AEs and SAEs

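### Two attributable but symptom-free QTcF events, or two isolated ALT stopping events, do not automatically trigger the study halt in Section 5.5, although two renal events do

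*Protocol*

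**What the plan says.** Section 5.5 sets two compulsory halts. The first is a single serious adverse event that the investigator attributes to the study drug. The second is a repeat rule: "If the same severe adverse event is observed in two subjects across all study parts", if attributable, dosing stops until a full safety review has taken place.

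Severity is an intensity grade in Appendix 4, 12.4.4: "Severe: An event that prevents normal everyday activities".

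Section 5.4.5 overrides that grade for the renal criteria. Attributable renal findings "will be nominally categorised as a severe adverse event and will constitute individual stopping criteria for subjects".

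The QTc and liver sections have no such sentence. Section 5.4.3 says "A healthy volunteer or patient that meets either bulleted criterion below will be withdrawn from the study". The liver rule in 5.4.2 discontinues treatment in healthy volunteers, and in patients without liver involvement or biochemical liver dysfunction, "with baseline liver chemistry within the normal reference range for ALT if they are reasonably attributable to GSK3039294". Appendix 2 (12.2.1 and 12.2.2) sets the threshold at ALT of at least 3 times ULN. It makes the event serious only if bilirubin is also at least 2 times ULN or INR is raised: ">35% direct bilirubin) or INR >1.5, Report as an SAE".

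Section 5.4, on individual withdrawal, refers to "The presence of severe AEs predefined as stopping criteria below in Section 5.5". Section 5.5 lists no such events.

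**The concern.** A two-subject rule exists to catch a repeated signal that would not stop a study when seen once. QTcF prolongation and isolated ALT elevation can both occur without symptoms, and both are important enough here to end an individual's treatment. Under the text as written, a second attributable case of either does not by itself pause dosing in the other subjects. It must first be graded severe, be called serious, or lead someone to suspend the study.

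The renal section shows that the authors knew how to bring silent laboratory findings into the repeat rule. The protocol does not say why the same step was not taken for QTcF and ALT.

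A Section 5.5 halt also has consequences that an informal pause lacks: a full safety review, and discussion with the regulatory authority before dosing resumes.

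**Working it through.** The protocol gives no operating characteristic for the halt rule, so there is no figure to reproduce. The check follows each criterion through the two triggers in 5.5. Every case is assumed to be attributable and symptom-free.

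| Individual criterion, met in two subjects | Severe by 12.4.4? | Declared severe in its own section? | Serious by definition? | Automatic halt under 5.5? |
|---|---|---|---|---|
| Phosphate below 0.8 mmol/L, confirmed (5.4.5) | No | Yes | No | Yes, two-subject rule |
| QTcF above 500 msec, or a rise above 60 msec in healthy volunteers (5.4.1, 5.4.3) | No | No | No | No |
| ALT at least 3 times ULN, normal bilirubin and INR (5.4.2, 12.2) | No | No | No | No |
| ALT at least 3 times ULN with bilirubin at least 2 times ULN (above 35% direct), or with INR above 1.5 | No | No | Yes | Yes, at the first case |

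1. **Severity.** The definition in 12.4.4 is functional. An ECG interval or an enzyme value without symptoms does not prevent daily activities.

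2. **Seriousness.** QTcF prolongation is not a listed criterion in 12.4.2. Item 6 of 5.4.1 covers only cardiovascular events that are already serious. For ALT, 12.4.2 g requires raised bilirubin or INR as well. The important-medical-event route in 12.4.2 f is open to both, but it rests on judgement.

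3. **Cross-references in 5.4.** The pointer to 5.5 for predefined severe events leads to a section that predefines none. The same sentence sends the reader to Appendix 3 for the SAE definition. Appendix 3 covers genetic research, and the definition is in Appendix 4. The pointer suggests that the individual criteria may have been meant to count as severe, but it does not make them so.

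4. **Other controls.**
   - Each Part B cohort has a sentinel through Day 7 (4.2.2.1). Part C has a renal and then a cardiac sentinel, each dosed for 21 days (4.2.3.1).
   - A safety review follows each Part B cohort (Synopsis). Cohort 4a and Cohort 5 start only if the preceding review is acceptable (4.2.2.3, 4.2.3).
   - The Dose Escalation Committee reviews ECG and laboratory findings before escalation or a move to the next part (10.7.1).
   - Data are reviewed on an ongoing basis (9.3.2), liver stopping events are reported to the sponsor within 24 hours (12.2), and the sponsor may suspend at any time (10.5).

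The compulsory items act before the rest of a cohort is dosed, or between cohorts and dose levels. None fixes what happens when a second case appears while the rest of a cohort is being dosed together. Cohort 4 subjects take their doses at home after in-patient discharge on Day 7 (Table 3), so that situation can arise.

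**The case against.** The strongest reply is that the difference is a risk-based choice. The NOAEL rests on urine biochemistry (4.6), nephrotoxicity has its own row in the risk table (4.6.1), and that table has no row for liver or for QT prolongation. The Synopsis reports no QTcF prolongation in Part A at 200, 600 or 1200 mg. This lowers the likely frequency of the problem. But the protocol nowhere gives it as the reason for treating the criteria differently, and the wording of 5.4 sits badly with it.

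Second, compulsory reviews and sentinels already deal with much of the risk. This stands and limits the point. If a first case occurs in one cohort and a second in the next, the first will already have passed through a required review. What remains is mainly repeat cases within one cohort.

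Third, an investigator may call a single QTcF event above 500 msec an important medical event, and one attributable SAE halts the study. That would be stricter than the proposed rule, but it is optional. The fix also keeps the attribution judgement. What it removes is dependence on the severity or seriousness grade.

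Fourth, the liver algorithm in 5.4.2 and Figure 5 in 5.4.4 are not shown. Figure 5 is titled as managing individual subjects by arrhythmia type, but an escalation step in either figure cannot be ruled out.

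A reader might also count Table 6, which applies to patients whose baseline ALT is already raised, as another isolated-ALT criterion. The text does not support that. The withdrawal column pairs ALT above 6 times ULN with raised bilirubin and does not say whether one or both are needed. If both are needed, it is not an isolated ALT event.

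**Conclusion.** The point holds in a limited form. On the text of 5.4.1 to 5.4.3, 5.5, 12.2 and 12.4, two attributable, symptom-free QTcF stopping events do not automatically halt the study. Nor do two isolated ALT elevations of at least 3 times ULN in healthy volunteers or in patients with normal baseline ALT. Two matching renal events do.

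The severity is minor. The gap is mainly two cases within one concurrently dosed cohort, where Part B cohorts aim for 6 completers and Part C enrols at least 12 patients.

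Two stronger conclusions might be inferred and should not be. The first is that dosing would continue unchecked after a second case. The investigator, the study team and the sponsor can all act, and liver events reach the sponsor within 24 hours. The second is a stated probability that the gap would matter. The protocol gives no event rates, so any such figure would rest on assumed ones. A simple calculation with a sentinel would also misrepresent a sentinel period that ends at Day 7 of a 21-day course.

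The conclusion assumes that 12.4.4 is applied as written and that the figures not shown contain no study-level halt.

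**What to change.** Add one sentence to 5.5: the same individual QTcF or ALT stopping criterion, met in two subjects and reasonably attributable to GSK3039294, triggers the temporary halt. Alternatively, carry the deeming sentence of 5.4.5 into 5.4.2 and 5.4.3 for attributable events. If the sponsor does intend only renal findings to count, 5.5 should say so and give the reason.

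In 5.4, point to 5.4.1 to 5.4.6 for the individual criteria and to Appendix 4 for the SAE definition.

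The change is one or two sentences and two cross-references in an amendment. The downside is an occasional extra temporary pause, with the safety review and regulatory discussion that 5.5 attaches to it.

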5.6. Subject and Study Completion

A completed subject is one who has completed all phases of the study including the final follow-up visit.

The end of the study is defined as the last subject's last visit.

6. STUDY TREATMENT

6.1. Investigational Product and Other Study Treatment

The term ‘study treatment’ is used throughout the protocol to describe any combination of products received by the subject as per the protocol design. Study treatment may therefore refer to the individual study treatments or the combination of those study treatments.

	Study Treatment
Product name:	GSK3039294 Capsules
Dosage form:	Capsules
Unit dose strength(s)/Dosage level(s):	20 to 200mg
Route of Administration	Oral
Dosing instructions:	Swallow with water as directed in the SRM
Physical description:	White, opaque capsule
Method for individualising dosage:	A single capsule or multiple capsules to be taken depending on the dosage required

6.2. Treatment Assignment

This is an open-label, non-randomised study with no active or placebo control.

GSK3039294 doses will be administered sequentially, as detailed in Section 4.1, and will be based on the review of safety, PK and PD data from previous cohorts, dosing sessions and study parts.

6.3. Planned Dose Adjustments

This protocol allows some alteration from the currently outlined dosing schedule, but the maximum daily dose will not exceed pre-clinical exposure limits (C_{max} of 22.1 µg/mL and AUC_[0-24] of 250 µg.hr/mL).

The decision to proceed to the next dose level of GSK3039294, will be made by the GSK Study Team and the investigator based on safety, tolerability and preliminary pharmacokinetic and/or pharmacodynamic data (Parts B and C) obtained in at least 6 subjects at the prior dose level (see Section 10.7.1). The actual doses to be administered may be adjusted based on safety, tolerability and preliminary pharmacokinetic and/or

pharmacodynamic data at previous dose levels; these dose adjustments may involve either an increase or a decrease in the planned dose.

The dosing schedule may also be adjusted to expand a dosing cohort to further evaluate safety, pharmacokinetic and/or pharmacodynamic findings at a given dose level, or to add cohorts to evaluate additional dose levels. The study procedures for these additional subject(s) or cohort(s) will be the same as that described for other study subjects.

6.4. Blinding

This will be an open-label, non-randomised, dose-escalation study with no active or placebo control.

6.5. Packaging and Labeling

The contents of the label will be in accordance with all applicable regulatory requirements.

6.6. Preparation/Handling/Storage/Accountability

A description of the methods and materials required for preparation of GSK3039294 will be detailed in a Study Specific Technical Agreement/Memo (TTS) or Pharmacy Manual which will be accompanied by a Quality Agreement.

- Only subjects enrolled in the study may receive study treatment and only authorized site staff may supply or administer study treatment. All study treatments must be stored in a secure environmentally controlled and monitored (manual or automated) area in accordance with the labelled storage conditions with access limited to the investigator and authorized site staff.
- The investigator, institution, or the head of the medical institution (where applicable) is responsible for study treatment accountability, reconciliation, and record maintenance (i.e. receipt, reconciliation and final disposition records).
- Further guidance and information for final disposition of unused study treatment are provided in the SRM.
- Under normal conditions of handling and administration, study treatment is not expected to pose significant safety risks to site staff. Take adequate precautions to avoid direct eye or skin contact and the generation of aerosols or mists. In the case of unintentional occupational exposure notify the monitor, Medical Monitor and/or GSK study contact.
- A Material Safety Data Sheet (MSDS)/equivalent document describing occupational hazards and recommended handling precautions either will be provided to the investigator, where this is required by local laws, or is available upon request from GSK.

